7. INVESTIGATIONAL PLAN

7.1. Overall Study Design

This is an open-label, multicenter, study to evaluate the efficacy and safety of eteplirsen in patients with genotypically confirmed DMD with exon deletions amenable to exon 51 skipping (treated group), as compared with an untreated control arm of DMD patients amenable to exon skipping (untreated control group).

Patients will be evaluated for inclusion during a Screening/Baseline period of up to 10 weeks (not including time needed for genotyping if the patient has not been previously genotyped). Eligible patients for the treated group will receive once weekly IV infusions of 30 mg/kg eteplirsen for 96 weeks, followed by a safety extension (not to exceed 48 weeks), until the product is commercially available or until patients can transition into a separate eteplirsen study. Eligible patients in the untreated control group will not receive treatment with eteplirsen, but will complete selected study assessments through 96 weeks.

For the treated group, eteplirsen will be administered once weekly via an IV infusion. It is recommended that a topical anesthetic cream (e.g., lidocaine 2.5%, prilocaine 2.5% or LMX4 cream) be applied to the infusion site prior to each administration of eteplirsen. An implanted venous access port may be inserted for eteplirsen administration at the discretion of the parent/legal guardian and the Investigator. Patients should be observed for possible reactions to the infusion for at least 1 hour after each infusion is completed. For visits where safety assessments are not being collected, optional in-home administration of eteplirsen by a visiting nurse may be available after Week 25.

[figure not shown]
For all patients, efficacy, including the 6MWT, will be assessed at regularly scheduled study visits by a blinded rater. To minimize assessment bias, every effort will be made to keep the clinical evaluators unaware of the treatment arm of the patients, and all biological efficacy endpoint evaluations will be performed by blinded assessors. Upon qualification for the study during the Baseline visit, patients in the treated group will undergo a muscle biopsy and will be randomized to a second muscle biopsy at Week 24, 48, 72, or 96 in a 1:2:1:1 ratio. Patients in the untreated control group will not undergo muscle biopsy at any time point.

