10.2.2. Baseline Period (3-5 Weeks after Screening Functional Assessment Visit)

The muscle biopsy should be the last Baseline procedure performed.

At Hub Sites (Baseline Functional Assessment Visit; occurs within 4 weeks prior to Week 1):

The Baseline period may require a 2-night overnight stay near the Hub Site. Assessments will begin in the mornings on Day 1 and Day 2 in the order described in the Clinical Evaluator Manual.

Day 1:

- Assess eligibility
- Vital signs
- Height and ulnar length
- CCI
- 6MWT (Pulse will be recorded immediately prior to and after the 6MWT.)
- NSAA
- CCI

Day 2:

- CCI
- 6MWT (Pulse will be recorded immediately prior to and after the 6MWT.)
- NSAA
- CCI

Either Day 1 or Day 2:

• ECG

At Surgical Units (After eligibility has been confirmed) (for the treated group only):

The muscle biopsy should be the last Baseline procedure performed after the Local Site has confirmed eligibility. Assessments at the Surgical Unit should be performed in the order described in the Clinical Evaluator Manual.

- Informed Consent
- Safety laboratory assessments, including chemistry, hematology, coagulation, and urinalysis
- Immunogenicity
- A muscle biopsy will be performed on all patients in the treated group. The biopsy may be obtained as soon as eligibility is confirmed (i.e., Baseline assessment is complete and genotype is confirmed), prior to the first dose of eteplirsen. The first dose of eteplirsen must be within 4 weeks of the Baseline Functional Assessment visit. Surgery must be performed within the 4-week window between the Baseline Functional Assessment visit and Week 1. Patients in the treated group may not begin to receive eteplirsen until after the Baseline muscle biopsy has been performed.

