11.3.2. Relationship to Study Procedures

For each AE the Investigator determines whether there is a reasonable possibility that the AE may have been caused by the study procedures according to the categories below:

Unrelated: The event is clearly not related to the study procedures

Possibly/probably related: The event could be related/is likely to be related to study

procedures

Definitely related: The event is clearly related to the study procedures

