13.10.2.1. Adverse Events

For treated patients, only TEAEs will be summarized. Non-treatment emergent events will be recorded in data listings. For all AE tables, the number and percent of patients reporting AEs (grouped by MedDRA SOC and PT) will be summarized by treatment group. In general, tables will have events categorized into all TEAEs and treatment-related TEAEs.

As untreated patients (control group) will have no TEAEs, AEs collected post-qualification for the study will be summarized similarly to treated patients' TEAEs. All captured AEs for this control group will be listed.

Multiple occurrences of the same AE (at the PT level) in the same patient will be counted only once in frequency tables. If a patient experiences multiple episodes of the same event with different relationship/severity, the event with the strongest relationship and maximum severity to IP will be used to summarize AEs by relationship and severity. Treatment-related TEAEs will be defined as those that the Investigator considers possibly/probably or definitely related to the IP.

The following summary tables will be produced:

- TEAEs
- TEAEs by severity
- Treatment-related TEAEs
- Treatment-related TEAEs by severity
- SAEs

In addition, all SAEs, regardless of their treatment-emergent status will be summarized by SOC and PT.

The following listings will be produced:

- Non-treatment emergent AEs
- All TEAEs
- AEs leading to discontinuation
- SAEs

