Treatment-emergent Adverse Event

An AE will be considered treatment-emergent if it occurs in the time period starting with the initiation of the first dose of eteplirsen and ending 28 days after the last dose of eteplirsen for eteplirsen-treated patients, or on or after the Week 1 visit date for untreated control patients.

To define treatment emergence for AEs with missing onset or stop date or time, the following additional criteria will be used:

If both start and stop dates for a particular AE are missing, then the AE is considered treatment emergent.

- If onset date for a particular AE is missing, and stop dates falls after the first date/time, then that AE is considered treatment emergent.

- If onset date for a particular AE is the same as the first dose date and the start times missing, and stop dates falls after the first date/time, then that AE is considered treatment emergent.

Treatment-related Adverse Event

A treatment-related AE is any AE reported on the ADVERSE EVENTS eCRF that is marked as definitely related, or probably/possibly related to study drug.

Treatment-emergent Laboratory Abnormality

A treatment-emergent laboratory abnormality will be defined as any laboratory abnormality occurring or worsening after the initiation of eteplirsen dosing and within 28 days of the last dose of eteplirsen for eteplirsen-treated patients or occurring or worsening on or after the Week 1 visit for untreated control patients.

Prior Medication

A prior medication will be any medication taken and completed prior to the first dose of eteplirsen for eteplirsen-treated patients, or before the Week 1 visit for untreated control patients.

Concomitant Medication

A concomitant medication will be any medication that is taken in the time period starting with the initiation of the first dose of eteplirsen dosing and ending 28 days after the last dose of eteplirsen for eteplirsen-treated patients, or on or after the Week 1 visit for untreated control patients.

Previous Drisapersen Exposure Status

A patient will be considered as having previous exposure to drisapersen if he had taken any drisapersen prior to Day 1 in this study (value=Yes); otherwise a patient will be considered as not having a previous exposure to drisapersen (value=No).

Time Since DMD Diagnosis

The time since DMD diagnosis, in months, will be calculated as (Day 1 – Date of DMD diagnosis + 1)/30.4375.

Duration of Corticosteroid Treatment

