- TEAEs reported in $\geq 10\%$ of patients in any treatment group (upon examination of the actual data, different cut-off points may be used to examine the incidence of these AEs if it is deemed appropriate)
- TEAEs reported in $\geq 2\%$ of patients in the active treatment group (and greater than untreated group)

The following listings will be produced:

- Listing of non-TEAEs
- Listing of TEAEs
- Listing of TEAEs leading to discontinuation of study drug
- Listing of TEAEs leading to withdrawal from study

Listings will include all data with an indicator for treatment period for each record when the event occurred.

Serious Adverse Events and Deaths

The following summary tables will be produced:

- treatment-emergent nonserious AEs
- treatment-emergent SAEs
- treatment-related, treatment-emergent SAEs
- deaths and AEs resulting in death
- AEs leading to study drug discontinuation by SOC and PT

The following listings will be produced:

- Listing of all AEs
- Listing of AEs leading to discontinuation
- Listing of SAEs (including pre-dosing SAEs)
- Listing of death
- Listing of SAEs that occurred prior to the initiation of study drug or after 28 days post-last dose will be excluded from the tables but will be included in the listing at the start date/time of the AE.
- Listing of AEs related to study procedure by SOC and PT

Listings will include all data with an indicator for treatment period for each record when the event occurred.

A summary of deaths and reasons for deaths will be presented by Analysis period and treatment group. A patient-level listing will be provided.

Adverse Events of Special Interest

Summaries of AEs of special interest will be summarized by SOC and PT. All standardised MedDRA Queries ([SMQs]) listed below will include broad and narrow terms. The AESI are:

- hypersensitivity (hypersensitivity SMQ)
- renal toxicity (acute renal failure SMQ)
- infusion-related reaction (IRR) (AEs occurring within 24 hours of the start of any infusion [including events occurring on the same date as an infusion where infusion start time or AE onset time was not reported])

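### SAP 7.9.1 tabulates only treatment-emergent SAEs, although Protocol 13.10.2.1 promises a summary of all SAEs, so a non-fatal pre-dose SAE from the Baseline biopsy would be listed but not tabulated

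*SAP*

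**What the plan says.** **Biopsies.** Treated boys have one muscle biopsy at Baseline and are randomized to a second at Week 24, 48, 72 or 96 (SAP 4.3). For controls, Protocol 7.1 says: "Patients in the untreated control group will not undergo muscle biopsy at any time point". Protocol 10.2.2 fixes the timing of the first biopsy: "Surgery must be performed within the 4-week window between the Baseline Functional Assessment visit and Week 1", and "Patients in the treated group may not begin to receive eteplirsen until after the Baseline muscle biopsy has been performed".

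**AE collection.** AEs are recorded from informed consent (Protocol 11.1). Protocol 11.3.2 adds a rating for procedures: "For each AE the Investigator determines whether there is a reasonable possibility that the AE may have been caused by the study procedures".

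**Protocol 13.10.2.1.** The general rule is "For treated patients, only TEAEs will be summarized", and events that are not treatment-emergent go to data listings. The section then makes a separate commitment for serious events: all SAEs are to be summarized by SOC and PT whatever their treatment-emergent status.

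**SAP 6.7.** For treated boys, "An AE will be considered treatment-emergent if it occurs in the time period starting with the initiation of the first dose of eteplirsen", and the window closes 28 days after the last dose. For controls it opens at the Week 1 visit. Undated events are also covered: "If both start and stop dates for a particular AE are missing, then the AE is considered treatment emergent".

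**SAP 7.9.1.** The two SAE tables are for treatment-emergent SAEs and for treatment-related, treatment-emergent SAEs. A bullet in the list of listings says that SAEs before study drug, or later than 28 days after the last dose, are left out of the tables and appear in the listing. The same list contains "Listing of AEs related to study procedure by SOC and PT".

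**The concern.** The protocol treats serious events as an exception to its TEAE-only rule, and the SAP removes that exception. The omission matters most before dosing, because that is when every treated boy has surgery done for research. Protocol 9.7 itself takes anesthesia in this population seriously: it bars depolarizing muscle relaxants and advises against volatile anesthetics because of rhabdomyolysis.

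At stake is a count. If a boy had a serious complication between the Baseline biopsy and the first infusion, the report would show it as a line in a listing. It would not appear in the SOC and PT summary that the protocol says will exist.

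**Working it through.** The plan states no figure on this point, so the check is a comparison of texts plus one count.

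**Step 1: the two rules side by side.**

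| Event in a dosed boy | Protocol 13.10.2.1 | SAP 7.9.1 |
|---|---|---|
| Non-serious AE, pre-dose | Listing | Listing |
| SAE, first dose to 28 days after last dose | Summarized | Tabulated |
| SAE, pre-dose | Summarized by SOC and PT | Listing only |
| SAE, more than 28 days after last dose | Summarized by SOC and PT | Listing only |

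The documents agree on the first two rows and conflict on the last two.

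**Step 2: follow a Baseline-biopsy SAE through the SAP.**
- Onset on or after the first dose: treatment-emergent, so tabulated.
- Both dates missing: treated as treatment-emergent, so tabulated.
- Onset before the first dose, fatal: possibly tabulated. The table of deaths and fatal AEs is not titled treatment-emergent, and deaths are also summarized by analysis period.
- Onset before the first dose, non-fatal: in neither SAE table. SAP 7.9.1 does not state a time window for the special-interest and additional-review summaries, which count SAEs among their events. They cover only selected event types and do not replace an all-SAE table.

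**Step 3: which end of the window matters.** For boys who discontinue, routine AE recording stops 4 weeks after the last infusion (Protocol 11.1), and 4 × 7 = 28 days. The late exclusion should therefore catch few routinely collected events. The pre-dose exclusion covers the whole interval from consent to first dose, including the surgery.

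**Step 4: scale.** Inputs are the planned numbers in SAP 4.2 and two biopsies per treated boy.
- Treated boys: 70 + 10 = about 80.
- Controls: 20 + 10 = about 30, with 0 biopsies.
- Planned biopsies: 80 × 2 = about 160.
- Biopsies before first dose: 80 × 1 = about 80, and 80/160 = one half.

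The documents give no rate of serious biopsy complications, so an expected number of untabulated SAEs cannot be derived from them.

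**Step 5: was the change declared?** The visible bullets of SAP 8.1 do not mention it. Two bullets are redacted, so the question stays open.

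**The case against.** The strongest reply has four parts.

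- **Nothing is lost.** Pre-dose SAEs are listed, and the listings carry a treatment-period indicator. This is true and rules out any claim of concealment. A listing is still not the summary by SOC and PT that the protocol specifies.
- **The SAP may depart from the protocol.** Protocol 13.1 provides for deviations to be set out in the SAP, and SAP 7.9.1 states its handling openly. This stands as far as it goes, but no reason for dropping the table is visible.
- **The exclusion sentence is badly worded.** It comes after tables already titled treatment-emergent and may only be explaining them. That is a fair reading. The all-SAE table would still be missing.
- **Pre-dose events say nothing about the drug.** Agreed, and the TEAE tables should stay as they are. The protocol asked for the all-SAE summary in addition to them.

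A reader might go further and infer that the lack of a table of procedure-related AEs is itself an error. The documents do not support that. Protocol 13.10.2.1 lists no such table and sends non-treatment-emergent events to listings, and the SAP adds a procedure-related listing by SOC and PT. The rating categories in Protocol 11.3.2 do not identify which procedure was responsible, so such a table could not isolate biopsy harms.

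A reader might also infer that second-biopsy AEs distort the by-arm tables. They do enter those tables beside a biopsy-free control group. However, safety is descriptive, SAP 8.1 rules out inferential comparison of the groups, and the documents give no event rates from which to size an effect.

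**Conclusion.** The point holds as a minor inconsistency between the two documents: the protocol promises a summary of all SAEs, and the SAP replaces it with treatment-emergent tables plus a listing. The practical consequence is that a non-fatal SAE from the Baseline biopsy with onset before dosing would appear in no SAE table. About 80 planned pre-dose biopsies are exposed to this gap. The number of events affected is unknown and may be zero.

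The conclusion rests on planned enrolment and on reading the SAP's SAE table titles literally. It does not extend to deaths, which may be tabulated, or to non-serious pre-dose AEs, for which a listing is what the protocol specifies. Nor does it support a charge of an undeclared change, given the redactions in SAP 8.1. No hypothesis test or efficacy estimate is affected.

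**What to change.** In SAP 7.9.1:

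1. Add one table of all SAEs by SOC and PT, by group, whether or not treatment-emergent. Preferably split it by onset before versus on or after first dose (Week 1 visit for controls).
2. Reword the exclusion sentence so that it applies only to tables titled treatment-emergent.

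If the sponsor prefers to keep the listing alone, SAP 8.1 should say so as a departure from Protocol 13.10.2.1.

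The cost is a few lines of SAP text and one extra descriptive table from fields already collected. One limit remains. On the Safety Set as both documents define it, a boy biopsied but never dosed would still appear only in listings; the documents give no count of such boys. A table of procedure-related AEs would be an optional addition and is not needed to resolve this point.

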11.4. Recording Adverse Events

All AEs/SAEs experienced from the time of informed consent/assent to the last follow-up will be recorded within each patient's CRF. Information should include: a concise description of the event; date and time of event onset and resolution; determination of seriousness, severity, corrective treatment, outcome, and relationship to IP or study procedure or underlying disease; and any action taken will be recorded. Resolution occurs when the patient has returned to his Baseline state of health or further improvement or worsening of the event is not expected.

Whenever possible, a diagnosis will be recorded as an AE, rather than symptoms or isolated laboratory abnormalities related to that diagnosis. Several symptoms or laboratory results that are related to the same diagnosis can thus be part of the same AE. A medical or surgical procedure is not an AE; rather the condition leading to the procedure should be recorded as the AE. Similarly, death is not an AE, but is rather the outcome of the AE(s) that resulted in death. If the AE(s) leading to death are not known, then death must be reported as an AE. All AEs will be followed until the resolution of AE, completion of the patient's study participation, or study termination, whichever occurs first. SAEs will be followed until resolution or until the condition stabilizes or returns to Baseline status.

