6.2.4 Imputation of Relationship or Severity for Adverse Events

In the summary of AEs, events with missing relationship or severity will be presented as "Related" or "Severe", respectively. However, missing values will be presented in the data listings as missing.

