Prior to statistical analysis, for all IRRs as defined above, IRRs will be medically reviewed by a pharmacovigilance physician. All IRRs as defined above that are considered as related to study drug by investigators will be counted in the list of medically reviewed IRRs. In addition, all IRRs as defined above that meet the following criteria will be excluded from the list of medically reviewed IRRs:

- AE was an infusion site, application site, or other local AE not associated with IRR
- AE had a clear alternate etiology that could be ascertained based on the reported event (eg, reaction to plaster, assessed as related to procedure or underlying disease by investigator)
- AE not associated with an IRR due to the nature of the event

Summaries of all medically reviewed IRRs and medically reviewed IRRs with event start time reported be generated separately. In addition, a summary table will be generated and include the following:

- Number of patients with medically reviewed IRRs
- Number of medically reviewed IRRs
- Number of medically reviewed IRRs with event start time reported
- Number of events on any day for medically reviewed IRRs

A corresponding listing will be generated for each table. Additionally, a table and listing corresponding to the AESIs that were related to study drug and/or moderate or severe will be produced. An overall summary of AESI events will include total number of events, number of SAEs, number of treatment-related events, number of unrelated events, number of mild events, number of moderate events, number of severe events, and number of events occurring on the same day as an infusion (within 24 hours or on the same day

with no time). A listing of each AESI category and a listing of AEs related to study drug for each AESI strategy will be generated.

Additional AEs for Review

Additional AEs for review will be summarized by SOC and PT All SMQs listed below will include broad and narrow terms. The AEs for additional review are:

- Drug-induced hepatotoxicities (cholestasis and jaundice of hepatic origin SMQ, hepatic failure, fibrosis, cirrhosis, and other liver damage-related conditions SMQ, hepatitis, noninfectious SMQ, liver neoplasms, benign [including cysts and polyps] SMQ, liver malignant tumors SMQ, liver tumors of unspecified malignancy SMQ, liver-related investigations, signs and symptoms SMQ, liver-related coagulation and bleeding disturbances SMQ)

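### When an onset or infusion time is missing, the infusion-reaction rule in SAP 7.9.1 leaves out next-day events that may lie inside its own 24-hour window

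*SAP*

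**What the plan says.** IRR is one of three adverse events of special interest in SAP 7.9.1, with hypersensitivity and renal toxicity. Its definition has two limbs. The first is a time window: "AEs occurring within 24 hours of the start of any infusion". The second is a fallback for incomplete records: "including events occurring on the same date as an infusion where infusion start time or AE onset time was not reported".

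The definition decides what is reviewed. The SAP states that "for all IRRs as defined above, IRRs will be medically reviewed by a pharmacovigilance physician". Events the investigator called related have a direct route onto the reviewed list, but with the same limit: "All IRRs as defined above that are considered as related to study drug by investigators will be counted in the list of medically reviewed IRRs".

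The overall summary of special-interest events uses the same convention. It counts the "number of events occurring on the same day as an infusion (within 24 hours or on the same day", and the parenthesis ends by tying the same-day part to records without a time.

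On missing times, Protocol 11.4 asks for the "date and time of event onset and resolution" of every event. The SAP still allows for gaps, because its IRR table has a row for the "Number of medically reviewed IRRs with event start time reported".

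**The concern.** A 24-hour window that opens during the day closes on the following date. The fallback stops at midnight. For a complete record the two limbs agree with the stated intent. For an incomplete record they do not: an event on the morning after an infusion counts as an IRR if both times are known, and does not count if either is missing.

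At stake is who sees the event. The planned review can remove an event that does not belong, but it cannot recover one that never reached it. Whether a next-day event is assessed as an IRR would depend on whether a clock time was entered, not on what happened to the patient.

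**Working it through.** The plan gives no figure on this point, so there is none to reproduce. The check applies the rule to test cases and then works out how much of the window the fallback can reach.

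**Inputs.** The window and fallback come from SAP 7.9.1, and weekly dosing from Protocol 9.3. The documents give no clock time for infusions, so every start time below is an assumption.

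**Step 1: the rule applied to cases.** The infusion is on day D.

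| Infusion start | Event date and time | Hours from start | IRR under SAP 7.9.1? |
|---|---|---|---|
| 10:00 | D+1, 07:00 | 21 | Yes |
| 10:00 | D+1, 11:00 | 25 | No |
| 10:00 | D, no time | Unknown; may precede the infusion | Yes, by date |
| 10:00 | D+1, no time | Between 14 and 38 | No |
| No time | D+1, 07:00 | 24 or less if the start was at 07:00 or later | No |

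The last two rows are the gap. In both, the event may be inside 24 hours, and neither limb admits it.

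**Step 2: does another rule bring these events in?** SAP 6.2.3 covers incomplete dates for medications, treatment emergence and baseline durations. SAP 6.7 covers missing dates and times for treatment emergence. SAP 6.2.4 says "events with missing relationship or severity will be presented as" related or severe, respectively. None of these decides IRR status, and the investigator-related route accepts only events that already meet the definition.

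**Step 3: share of the window on the next date.** For a start at hour h, the part of the 24 hours after midnight is h/24.

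- 08:00: 8/24 = 33%
- 10:00: 10/24 = 42%
- 12:00: 12/24 = 50%
- 14:00: 14/24 = 58%
- 16:00: 16/24 = 67%

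**Step 4: what a next-day rule would let in.** An untimed event on D+1 began between 24 − h and 48 − h hours after the start: 16 to 40 hours for an 08:00 start, 8 to 32 hours for a 16:00 start. The part of D+1 beyond the window is (24 − h)/24, which is 67% at 08:00 and 33% at 16:00. With weekly infusions, capture by date alone would go from 1 day in 7 (14%) to 2 days in 7 (29%).

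**The case against.** The case for leaving the rule alone has several parts.

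- **Missing times should be uncommon.** Onset time is required, Protocol 12.1 plans full source data verification, and Protocol 12.2 plans checks and queries for missing data. This stands, and it limits the problem to incomplete records.
- **The fallback is already inclusive.** It admits untimed same-date events that may have begun before the infusion. A reader might set it against SAP 6.2.4 and infer that the SAP departs here from its cautious handling of missing data. That is too strong: the fallback leans the same way but stops one date short.
- **The wording is inclusive, not exclusive.** The bracket adds a class of events and does not expressly bar others. But 24 hours cannot be verified without both times, and the special-interest summary repeats the same-day limit, so a programmer would have no basis for admitting a next-day event.
- **The events stay visible.** They appear in the tables and listings of treatment-emergent events, and count as hypersensitivity events of special interest if their terms match that query. This stands. What they lose is the IRR label and its review.
- **Widening the rule brings in false positives.** Step 4 confirms this, and the three exclusion criteria for the review do not screen on timing. This is a good reason not to merge next-day events into the main count.

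Two stronger readings are tempting. One is that a third to two thirds of IRRs would be lost. The percentages are shares of clock time; they would be shares of events only if every record lacked a time and onsets were spread evenly over 24 hours, and the documents say neither. The other is that delayed reactions as a class go uncounted. Next-day events with both times recorded are counted, and an untimed event 12 hours after a start before noon falls on the same date and is counted too. One might also suppose that next-day events, arising away from the site, more often lack a time. That is plausible, but the documents do not show it.

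**Conclusion.** The gap is real and narrow. When the onset time or the infusion start time is missing, an event dated the day after an infusion cannot become an IRR under SAP 7.9.1 and is not sent to the physician review, whatever the investigator's causality assessment. This follows from the text and needs no assumption about start times.

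Its size in events is unknown, because the documents give neither the frequency of missing times nor the distribution of onsets. The 33% to 67% range shows only how much of the window the fallback cannot reach for assumed starts between 08:00 and 16:00. Safety analyses are descriptive (SAP 7.9), so no hypothesis test or efficacy result depends on this count. It merits correction because it affects the completeness of a named event of special interest and is cheap to close.

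**What to change.** Add a rule to SAP 7.9.1 before the review list is drawn: an adverse event dated the calendar day after an infusion, with onset time or infusion start time missing, also goes to the pharmacovigilance review unless the time that is recorded rules out the 24-hour window.

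In practice that exception applies when the event is timed and the infusion is not. An event at 22:00 on the next day, for example, would need a start at 22:00 or later. The SAP should say what evidence is enough to apply it.

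Keep the current definition for the main IRR count. Report the next-day, date-only events that survive review as a separate row or sensitivity count, including those the investigator considered related. They should not pass into the main list through the investigator-related route. The planned rows for all reviewed IRRs and for those with a start time already give, by difference, the number without an onset time, so the extra display is small.

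The cost is one or two sentences, one table row and a few more events to review. Some will have begun more than 24 hours after the infusion started, and the review criteria cannot identify which. That is why they belong in a separate row.
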